#### **VNS Health Total Member or FCP screening questions (Aims 1 and 2)**

1. Are you over 18 years of age?
2. Do you, or does a member of your family, receive health care from [VNS Health Total's/current plan name] Medicare Advantage plan?
3. Please name as many animals as you can in one minute. (Write down every animal mentioned. Must name 15 different animals)

#### **6. CONSENT FORMS AND ADDITIONAL PHI AUTHORIZATIONS.**

Prior to participating in any Aim (Aim 1, Aim 2, or Aim 3) study activities, all members, FCP, CBPC team member, and research/content expert participants will provide informed consent. Informed consent will be obtained by study personnel in person, by telephone, via oral consent. We are requesting this alteration of written consent in order to reduce the burden on participants of meeting in-person and to be able to include individuals in the study who may not have access to technology to provide e-consent. After obtaining oral consent over the phone, the study team will mail or email a copy of the form to the participant. Informed consent will be conducted by study personnel trained in consent procedures. Study personnel will review the study, allowing the participant to ask questions at any time during the discussion. The main points addressed by study personnel include explaining that participation is voluntary, why the study is being done, study procedures, potential risks and benefits of participation, and how participant confidentiality will be protected. Study team members will track oral consent in a secure, HIPAA compliant database such as REDCap that only authorized study personnel are able to access.

A copy of the study oral consent procedures are included in the application package.

## **7. REQUEST FOR WAIVER OF AUTHORIZATION**

In addition to obtaining consent from FCP, CBPC team member and research/content expert participants, we are requesting a waiver of consent and HIPAA authorization to access VNS Health Total member electronic records for the following reasons.

**Planning.** We will extract information about refusals of CBPC in the electronic health record such as the number of individuals who refused CBPC, their demographics, and health information (e.g., key diagnoses, triggering events that made them eligible for CBPC). Analyzing this information will allow us to improve information about risk for CBPC and who is refusing services so that we can create information materials and process 1) to support CBPC enrollment, particularly for PLwD and 2) that can be tested in other healthcare settings. As this extraction will involve several hundred records, including for deceased individuals, it is not possible to obtain this information without a waiver of authorization.

**Aims 1-2.** We request the waiver for VNS Health study staff to view electronic records of VNS Health Total members to identify VNS Health Total members and FCP who are potentially eligible to participate in Aims 1 and 2 of the study. It is not possible to identify potentially eligible members or FCP without the waiver of authorization.

**Aim 3.** We request the waiver for VNS Health study staff to view identification, enrollment, and refusal data. The information will be used to calculate CBPC refusal rates before and after intervention delivery and to analyze factors associated with CBPC enrollment and refusal in multivariable statistical modeling (described below).

A Request for Waiver of Authorization Form is included in the appendix of this application.

## **8. DATA TO BE EMPLOYED**

Please see Table 1 (above) and Appendix for data collection instruments at the end of the document. Data collection procedures will be conducted by trained research staff and done in-home, at VNS Health headquarters, at Rutgers University, by phone, by videoconference or online surveys as outlined in the protocol above. Data will be collected by research staff or online questionnaires and entered into and stored in a HIPAA compliant database such as REDCap.

## **9. ANALYTIC METHODS.**

### **Feasibility/Acceptability.**

We plan to conduct a pre/post pilot clinical trial to determine the feasibility and acceptability of an intervention to introduce tailored informational materials into clinician's discussions about community-based palliative care with VNS Health Total members who are eligible for the service. The informational materials will be tailored to the individual's risk profile as identified by a validated 12-month mortality risk algorithm. To establish feasibility and acceptability we will assess clinicians' and family care partners' assessments of the utility of the informational materials using the End-User Satisfaction Tool. End-User Satisfaction ratings for each concept are scored as 1 (almost never); 2 (some of the time); 3 (about half the time); 4 (most of the time); 5 (almost always). Minimum score is 12; maximum 60. Cumulative testing has produced percentile scores where a score of 54 corresponds to the 70th percentile. 57 = 80th and 59 = 90th. Short range test-retest scores for the overall score were .96 and the five subscales ranged from .80 to .95. Long range test-retest scores were .85 overall and .60 to .82 for the subscales. (Appendix). We will also assess whether and how the CBPC team members use the intervention (informational materials about palliative care) at regular intervals to assess fidelity and feasibility.

### **Qualitative analysis.**

For Aims 1 and 2, We believe sample sizes will be sufficient to obtain thematic saturation in qualitative analyses. If needed, we will continue to collect data at all stages until achieving thematic saturation. Interview

and focus group data will be transcribed and imported into qualitative data analysis software for analysis (e.g., nVivo, Dedoose). Data coding and analysis will be informed by a responsive model in which blocks of information are combined based on the theme they represent. Trained raters will independently review the transcripts and identify passages that include suggestions for inclusion and/or modifications to the intervention. Raters will then organize these passages into categories reflecting single themes, discuss these themes, and revise themes until consensus is reached. Additionally, a study team member will take notes during stakeholder interviews and focus groups. Relevant notes and written feedback from stakeholders will be incorporated into developing a set of informational materials and process for individualizing information provision about potential benefits of CBPC, particularly for PLwD and FCPs.

### **Quantitative Analysis.**

For Aim 3, based on 2022 identification, eligibility, and refusal data, we anticipate 500 individuals will be identified as eligible for CBPC during the study period (250 control, 250 intervention) and that 80 individuals will refuse CBPC during the pre-test/control period. Of these, 365 CBPC-eligible and 60 refusals are expected to be PLwD.

We will use descriptive statistics to describe the sample. End-user satisfaction results will be reported as mean ratings for each item and across all items as a composite score. Results will also be reported by percentages of respondents by Likert scale level, as well as grouped by percent favorable and unfavorable. Percentage of clinicians finding the intervention to be feasible and acceptable and the proportion reporting using the informational materials will be calculated.

Additionally, we will determine the association between the intervention and reductions in refusal of CBPC among eligible individuals. We will use a pre/post design for this pilot clinical trial. For the pre-intervention measurement, we will calculate the number of palliative care services refusals among all palliative care-eligible VNS Health Total members (expected n=250) for a 6-month lookback period prior to introducing the informational materials into clinical practice. For the post-intervention measurement, after incorporating the informational materials into clinical practice, we will observe palliative care refusals prospectively for 6 months among all palliative care-eligible VNS Health Total members (expected n=250). We hypothesize that the number of refusals will decrease during the 6-month intervention period.

We assume we will see approximately 80 refusals among the 250 pre-intervention patients, for a refusal rate of  $80/250 = 0.32$  (or 32%) or  $H_0 = p_{pre} \geq p_{post}$ , where  $p_{pre}$  and  $p_{post}$  are the pre and post intervention CBPC refusal rates, respectively.

The table below show the post-intervention CBPC refusal rates we will be able to detect, for different power levels, assuming a total of 500 patients (250 pre, 250 post) a significance level  $\alpha = 0.05$ , and a pre-intervention CBPC refusal rate of 0.32.

Power	Pre-intervention CBPC refusal rate	Post-intervention CBPC refusal rate	Absolute rate reduction	Percent rate reduction
0.80	0.32	0.206	0.114	35.6%
0.85	0.32	0.199	0.121	37.8%
0.90	0.32	0.190	0.130	40.6%
0.95	0.32	0.178	0.142	44.4%

With 80% power, we will be able to detect a 11.4 percent points (or 35.6%) reduction of the CBPC refusal rate between pre and post intervention.

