**Table 1.**

Domain	Proposed measure (items)	Aims	Schedule	Participants
Demographic and Health Information	Age, sex, race, ethnicity, education level, perceived discrimination in healthcare encounters (FCP only), relationship to VNS Health Total member (FCP only), role on CBPC team (CBPC team members only), etc.	1-2	Baseline (Aim 1)	VNS Health Total members, FCP, CBPC team members, research/content experts (Aim 2 only)
	Age, sex, race, ethnicity, date of CBPC eligibility determination, date of CBPC refusal, diagnoses, triggering events	3	As extracted from electronic health record for pilot clinical trial analysis	VNS Health Total CBPC-eligible members
Knowledge of Palliative and Hospice Care	Palliative Care Knowledge Survey  additional questions on palliative care knowledge and attitudes 9/26/2025 8:41:00 PM	1-2	Baseline (Aim 1), following feedback on intervention materials (Aim 2)	VNS Health Total members, FCP
Intervention Development	Interview guides with questions about palliative care experiences, knowledge, barriers to participation in CBPC, including 5 rights framework (Aim 1); and user-centered design questions to solicit feedback on intervention materials (Aim 2)	1-2	1-time interview for Aim 1. 1-time think aloud session for Aim 2	VNS Health Total members, FCP, CBPC team members, research/content experts (Aim 2 only)
Intervention Feasibility and Acceptability	PC team member reports of use of intervention	3	1, 3, and 6 months into intervention delivery (Aim 3)	CBPC team members
	End-User Satisfaction Survey 	1, 3	Baseline (Aim 1); 1, 3, and 6 months into intervention delivery (Aim 3)	CBPC team members
Primary Endpoint	Number and rate of CBPC refusals (denominator=number of CBPC-eligible individuals)	3	As extracted from electronic health record for pilot clinical trial analysis	VNS Health Total CBPC-eligible members

**Data Collection Protocol.** Survey responses for Aims 1-3 will be collected in two ways: online or by telephone. Whenever possible, participants will be sent surveys to their preferred emails via REDCap, a password protected, HIPAA compliant data management system. Survey links will be unique to study

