### **Clinical Trial.**

*PC team member Recruitment.* All of the CBPC team members who present the CBPC program to CBPC-eligible individuals and FCP will be asked to use the informational materials developed as part of this project when speaking with VNS Health Total members and FCP about the CBPC program. We will work with the CBPC leadership to identify effective ways to engage CBPC team members in the intervention while minimizing potential burden. CBPC team members who deliver the intervention (i.e., use the informational materials when explaining CBPC to eligible individuals and their FCP) will be asked to complete fidelity, feasibility, and acceptability measures (e.g., End User Satisfaction Survey) at 1, 3, and 6 months into intervention implementation.

*VNS Health Total Member Recruitment.* We plan to conduct a pilot clinical trial of integrating tailored informational materials on the benefits of community-based palliative care for eligible persons based on their individualized profile as identified by a validated 12-month mortality risk algorithm. Based on recent VNS Health Total data regarding the number of individuals identified as eligible for palliative care, we expect to run the pilot clinical trial with 500 eligible individuals over an enrollment period of 12 months. This sample of 500 individuals included in the Inclusion Enrollment Table represents all individuals expected to be identified as eligible for palliative care during the study period (250 prior to intervention implementation and 250 following intervention implementation).

All data collection from VNS Health Total members for the pilot trial will be taken from existing electronic health records and remotely collected. For the pilot trial, the study team will not interact directly with palliative care-eligible individuals, or their FCP. All outcomes for VNS Health Total members will be captured through an existing data source (the VNS Health Total electronic record) under a waiver of informed consent (see below).

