*Retention.* To engage CBPC team members throughout the course of the intervention, we will present the informational materials at interdisciplinary team (IDT) and other team meetings prior to their introduction into clinical practice. We will also solicit feedback on introducing the intervention to the CBPC team members from the CBPC leadership team. Additionally, as part of the intervention development process, we will solicit feedback from CBPC team members about the best way to make the informational materials available and accessible to them. We will check in with CBPC team members monthly in order to ascertain how intervention use is progressing, troubleshooting issues, and responding to CBPC team member concerns regarding material content and or accessibility.

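### The Aim 3 primary endpoint counts every eligible member without a recorded refusal as a non-refusal, and no planned by-period check separates fewer refusals from more unresolved conversations

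*Combined protocol and SAP*

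**What the plan says.** Table 1 (Section 3) defines the primary endpoint as "Number and rate of CBPC refusals (denominator=number of CBPC-eligible individuals"), extracted from the electronic health record. The member-level items it lists for Aim 3, apart from age, sex, race and ethnicity, are "date of CBPC eligibility determination, date of CBPC refusal, diagnoses, triggering events". Dates of offer, acceptance or enrollment are not listed, nor is any pending status.

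Section 9 (Quantitative Analysis) states for the period before launch that "we will calculate the number of palliative care services refusals" over a 6-month lookback, and for the period after it that "we will observe palliative care refusals prospectively for 6 months". The hypothesis is a decrease. Both periods use the same source. Section 5 (Clinical Trial) says: "All outcomes for VNS Health Total members will be captured through an existing data source (the VNS Health Total electronic record").

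On delivery, Section 5 says: "All of the CBPC team members who present the CBPC program to CBPC-eligible individuals and FCP will be asked to use the informational materials". Under Retention it adds: "We will check in with CBPC team members monthly in order to ascertain how intervention use is progressing". Surveys follow at 1, 3 and 6 months. Section 3 explains that randomizing team members is not feasible, so the comparison is pre-post.

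Two further places matter. Section 2 describes Aim 3 in terms of impact on CBPC enrollment. Section 7 requests a waiver so that staff can "view identification, enrollment, and refusal data" and mentions multivariable modeling of factors associated with enrollment and refusal. Section 9 does not specify that model, and it does not compare enrollment between periods.

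**The concern.** An eligible member can end the observation window in at least three states: enrolled, refused, or neither. The endpoint separates only the second from the other two. If launch changes how often a conversation ends in a recorded refusal rather than being left open, the refusal rate moves even when the number who enroll does not.

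The design has nothing to absorb such a shift. The presenting staff cannot be blinded to period, their use of the materials is followed up only after launch, and no concurrent group shows what recording would have looked like otherwise. More open conversations after launch would push the result toward the hypothesis.

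At stake is the meaning of a positive result. A significant fall in refusals would naturally be read as better uptake, and the planned primary comparison could not tell that apart from a larger unresolved group.

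**Working it through.** **Inputs.** Section 9 gives 250 eligible members per period, 80 pre-intervention refusals (80/250 = 0.32) and α = 0.05. It names no test and does not state sidedness. The documents give no figure for refusals left unrecorded, so that share, m, is an assumption and is varied below.

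**The plan's own figure.** The 80% power row sets 0.32 against 0.206. With a pooled two-sided z test and continuity correction 1/n:
- Mean proportion = (0.32 + 0.206)/2 = 0.263.
- Null SE = √(0.263 × 0.737 × 2/250) = 0.0394.
- Alternative SE = √[(0.32 × 0.68 + 0.206 × 0.794)/250] = 0.0390.
- Power = Φ[(0.114 − 0.004 − 1.96 × 0.0394)/0.0390] = 0.80.

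The other rows give 0.849, 0.901 and 0.948 against the stated 0.85, 0.90 and 0.95. The table therefore reproduces as two-sided and continuity-corrected, and its arithmetic is not at fault.

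**How many unrecorded refusals reach p < 0.05.** Hold decisions at 80 refusals in each period and let k post-launch refusals go unrecorded.
- k = 20 gives 60/250 = 0.24. Pooled proportion = 140/500 = 0.28; SE = √(0.28 × 0.72 × 2/250) = 0.0402; z = 0.08/0.0402 = 1.99; two-sided p = 0.046. With continuity correction, or with Fisher's exact test, p = 0.058.
- k = 21 gives 59/250 = 0.236. Uncorrected p = 0.036; p = 0.046 with continuity correction or Fisher.
- If the test were one-sided, k = 17 (63/250) gives p = 0.046.

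Twenty of 80 is 25% of refusals, or 20/6 ≈ 3 a month.

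**Chance of a false significant fall.** Take pre-launch counts as Binomial(250, 0.32) and post-launch counts as Binomial(250, 0.32 × (1 − m)). The probability that the uncorrected z exceeds 1.96, from exact binomials, is:

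| m (assumed) | Unrecorded, of 80 | Expected post rate | P(significant fall) |
|---|---|---|---|
| 0 | 0 | 0.320 | 0.025 |
| 5% | 4 | 0.304 | 0.06 |
| 10% | 8 | 0.288 | 0.12 |
| 15% | 12 | 0.272 | 0.22 |
| 20% | 16 | 0.256 | 0.35 |
| 25% | 20 | 0.240 | 0.51 |
| 30% | 24 | 0.224 | 0.68 |

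The full planned reduction of 0.114 corresponds to 0.114 × 250 = 28.5 unrecorded refusals, or 35.6% of 80.

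**The case against.** The strongest reply is that the contrast between periods is thin. Both use the same existing record, so recording is routine before and after launch, and observing prospectively describes timing rather than a new method of capture. Section 10 says the study leaves the procedure for identifying and approaching previously offered members unchanged and alters only the information given. The monthly check-ins concern use of the materials and do not mention refusal counts. Staff may also have known of the project during the lookback, since team members take part in Aims 1 and 2 and see the materials before launch. All of this stands. What differs by period is delivery of the materials and follow-up of their use, not the data source.

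A reader might infer that the presenting team records refusals and would relabel them as deferred. The documents do not say who makes the entry or whether a deferred status exists. Section 3 refers measure details to an Appendix that is not in the text available, so a definition of refusal there cannot be excluded.

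A reader might also infer that nothing in the data could reveal such a shift. Section 7 contradicts this: enrollment data will be accessed, and a fall in refusals without a rise in enrollment would be visible in them. The gap is that no by-period comparison of enrollment is pre-specified.

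Finally, moving from refusal to undecided may be a genuine effect of better information. That is a reason to report it under its own name, not to count it as uptake.

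**Conclusion.** The point holds as an unguarded risk. The endpoint puts unresolved members together with enrolled ones, the presenting staff know the period, there is no concurrent control, and no pre-specified analysis by period separates the two explanations for a fall. The documents do not show that any such shift occurs, or how large it would be.

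Its size depends wholly on the assumed share. At 5% to 10% of post-launch refusals unrecorded, the chance of a false significant fall is about 0.06 to 0.12 rather than 0.025. A quarter unrecorded is enough for p = 0.046 at the expected counts without correction, and 21 of 80 are needed with a continuity correction or Fisher's test. These figures assume a true refusal rate of 0.32 in both periods and 250 members in each.

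The plan should be changed on this point, because the result would otherwise be open to two readings and the data to choose between them are largely within reach.

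**What to change.** 1. State one coding rule for a refusal and apply it to both periods. Take each member's status at the same pre-specified interval from the eligibility date. A single late extraction of the latest status would not do: if the periods adjoin and the data are pulled when the second closes, pre-launch members have had about 6 to 12 months to resolve and post-launch members 0 to 6, so more of the latter would be unresolved through shorter follow-up alone.
2. Using the enrollment data already covered by Section 7, tabulate enrolled, refused and neither by period, and report the enrollment rate beside the refusal rate.
3. Add a sensitivity analysis that counts neither as not accepting in both periods. With the same denominator this is one minus the enrollment rate, so it needs no further data.
4. Describe a fall in refusals as improved uptake only if enrollment rises. Otherwise report it as a shift to unresolved status.

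The cost is one more tabulation, one sensitivity analysis, and a slightly later data cut so that the last post-launch members complete the interval. The result may also be less favorable than the refusal rate alone.

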### 3. STUDY DESIGN

The study proposes to identify barriers to CBPC enrollment and develop ways to use the information from a valid, accurate data-drive algorithm to address barriers to enrollment. The study will 1) develop informational materials for CBPC team members that can be used to explain CBPC in a manner tailored to a patient's algorithm-identified risk profile (the intervention), and 2) pilot test whether the informational materials have an impact on CBPC uptake among patients who previously refused CBPC. This study will use a multi-methods design including data collection and pilot testing.

To achieve **Aim 1** focus groups and interviews with CBPC team members, VNS Health Total members, and FCP will be conducted to identify items important in accepting and refusing CBPC.

For **Aim 2** we will develop the intervention. The intervention is a set of information materials that address CBPC generally and challenges that CBPC can help manage. The materials will be tailored to patient needs based on their algorithm identified risk profile (e.g., disease progression, medication, and symptom management). The materials will be used by CBPC team members when introducing and describing the CBPC program to VNS Health Total members and FCP.

Aims 1 and 2 participants will not be offered any services. They will be asked about their understanding of palliative and why they chose not to accept it in the past. Their responses will be used to improve how palliative care services and programs are explained to others in the future.

For **Aim 3** we will compare intervention and usual care CBPC refusal rates and assess CBPC team member and FCP satisfaction with intervention materials using the End-User Satisfaction Tool. Because of the size of the CBPC clinical team and workflow structure, it is not feasible to randomize CBPC team members to intervention or control groups. As such, we will use a pre-post pilot clinical trial to test the feasibility and efficacy of the informational materials and process, compared to usual practice, on CBPC refusal rates. We will retrospectively examine CBPC refusal rates (CBPC refusals/CBPC eligible individuals) for a 6-month lookback

period prior to implementing the intervention (informational materials and process). We will compare this rate of refusal to the CBPC refusal rate for a 6-month period after implementing the intervention.

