### **10. STATEMENT OF THE RISKS/BENEFITS FOR THE STUDY SUBJECTS.**

This is a minimal risk study to develop and pilot test the feasibility and acceptability of an intervention consisting of informational materials and processes to encourage acceptance of CBPC services. We will also assess the extent to which using the informational materials is associated with reductions in rates of CBPC refusal.

**Aim 1. Engage FCPs and CBPC team members to identify barriers to CBPC enrollment.** We do not anticipate that participants will benefit directly from providing feedback. Risks to study participants are minimal

and may include FCP becoming distressed when discussing why they refused palliative care for themselves or their loved one or becoming fatigued when participating in a one-hour interview.

**Aim 2.** Develop informational materials for CBPC team members to use when speaking with patients and FCPs about CBPC and process for tailoring information delivery based on patient's algorithm-identified risk profile. The purpose of this aim is to develop a set of informational materials and process for individualizing information provision about potential benefits of CBPC to PLwD and other patient populations and FCPs (NIA model Stage 1A). We do not anticipate that participants will benefit directly from providing feedback. They may become fatigued when providing feedback on the materials.

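### The only formal null for the primary endpoint points the wrong way, and its one-sided form beside an unqualified alpha of 0.05 does not match the power table, which reproduces at two-sided 0.05

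*Combined protocol and SAP*

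**What the plan says.** Table 1 (Section 3) labels the refusal outcome as the primary endpoint: "Number and rate of CBPC refusals (denominator=number of CBPC-eligible individuals". Section 3 says of the two six-month periods: "We will compare this rate of refusal to the CBPC refusal rate for a 6-month period after implementing the intervention".

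Section 9, Quantitative Analysis, gives the direction: "We hypothesize that the number of refusals will decrease during the 6-month intervention period". It takes 80 refusals among 250 pre-intervention patients (0.32), defines p_pre and p_post as the refusal rates before and after the intervention, and writes the null as "H_0 = p_{pre} \geq p_{post". No alternative is written. Alpha is given as 0.05, without one-sided or two-sided. The analysis itself is described only as "we will determine the association between the intervention and reductions in refusal of CBPC among eligible individuals".

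The power table assumes 250 patients per period and lists detectable post-intervention rates of 0.206, 0.199, 0.190 and 0.178 at 80, 85, 90 and 95% power, with columns for the absolute and percent reduction. The sentence after it reads: "With 80% power, we will be able to detect a 11.4 percent points (or 35.6%) reduction of the CBPC refusal rate". Section 10 says the study will assess "the extent to which using the informational materials is associated with reductions in rates of CBPC refusal".

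**The concern.** There are two faults in one line.

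**Direction.** The trial hopes to show p_pre > p_post. The printed null is p_pre ≥ p_post, so the hoped-for result is part of the null. Its complement, p_pre < p_post, is an increase in refusals. Followed literally, the rule could never support the study's hypothesis.

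**Match with the power table.** A directional null beside a bare 0.05 reads most naturally as a one-sided 0.05 test. If the table was computed for something else, the hypothesis and the power statement describe different tests, and turning the sign round would not reconcile them.

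At stake is the coherence of the only formal hypothesis for the primary endpoint. The pre-intervention half of the comparison is a retrospective lookback, which is a further reason to have the rule correct in writing before the post-intervention data arrive.

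**Working it through.** **1. Direction.** These statements in the plan can be set side by side:

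| Place | Direction |
|---|---|
| Section 9, hypothesis | p_post < p_pre |
| Section 9, table columns | reduction, p_pre − p_post > 0 |
| Section 9, sentence after the table | reduction of 11.4 points |
| Section 10, opening paragraph | reduction |
| Section 9, printed null | p_pre ≥ p_post, so rejection means p_post > p_pre |

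Only the null disagrees. Taken literally at one-sided 0.05, with a true post rate of 0.206, an uncorrected z test would reject with a probability of about 0.000003.

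**2. Inputs for the power check (all from Section 9).** n = 250 per period, p_pre = 0.32, alpha = 0.05. Assumed: two independent samples.

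Normal approximation with pooled variance under the null:

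power = Φ[(d − c − z·SE0) / SE1]

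- d = p_pre − p_post
- c = 1/n = 0.004 with continuity correction, 0 without
- SE0 = √(2·p̄(1 − p̄)/n), where p̄ is the mean of the two rates
- SE1 = √([p_pre(1 − p_pre) + p_post(1 − p_post)]/n)
- z = 1.960 for two-sided 0.05 (or one-sided 0.025), 1.645 for one-sided 0.05

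**3. The 80% row (p_post = 0.206).** d = 0.114, p̄ = 0.263, SE0 = 0.03938, SE1 = 0.03905.

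- Two-sided, corrected: (0.110 − 1.960 × 0.03938)/0.03905 = 0.84, power 0.800. This reproduces the plan.
- Two-sided, uncorrected: (0.114 − 1.960 × 0.03938)/0.03905 = 0.94, power 0.827.
- One-sided 0.05, corrected: (0.110 − 1.645 × 0.03938)/0.03905 = 1.16, power 0.877.
- One-sided 0.05, uncorrected: (0.114 − 1.645 × 0.03938)/0.03905 = 1.26, power 0.896.

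**4. All rows: power at the printed rates.** The Fisher figures come from exact binomial enumeration.

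| Stated power (p_post) | Two-sided, corrected | Two-sided, Fisher | Two-sided, uncorrected | One-sided 0.05, corrected | One-sided 0.05, Fisher | One-sided 0.05, uncorrected |
|---|---|---|---|---|---|---|
| 0.80 (0.206) | 0.800 | 0.801 | 0.827 | 0.877 | 0.879 | 0.896 |
| 0.85 (0.199) | 0.849 | 0.851 | 0.872 | 0.912 | 0.914 | 0.927 |
| 0.90 (0.190) | 0.901 | 0.902 | 0.918 | 0.946 | 0.947 | 0.956 |
| 0.95 (0.178) | 0.949 | 0.950 | 0.959 | 0.974 | 0.975 | 0.980 |

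**5. The same check, solved for the detectable post rate** at 80/85/90/95% power:

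- Printed: 0.206 / 0.199 / 0.190 / 0.178
- Two-sided 0.05, corrected: 0.2060 / 0.1989 / 0.1902 / 0.1775
- Two-sided 0.05, Fisher: 0.2062 / 0.1992 / 0.1905 / 0.1779
- Two-sided 0.05, uncorrected: 0.210 / 0.203 / 0.194 / 0.181
- One-sided 0.05, corrected: 0.218 / 0.210 / 0.202 / 0.189
- One-sided 0.05, uncorrected: 0.221 / 0.214 / 0.205 / 0.192

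The first two computed lines agree with the plan to within 0.001. Under one-sided 0.05 with continuity correction, the 80% figure would be 0.32 − 0.218 = 0.102, and 0.102/0.32 = 31.9%, against the stated 11.4 points and 35.6%.

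**6. When sidedness would matter.** If the pre-period gives 80/250 as planned, Fisher's two-sided p is 0.058, 0.073 and 0.092 at 60, 61 and 62 post-period refusals out of 250. The one-sided p is 0.029, 0.037 and 0.046. The two rules part only in that narrow band.

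**The case against.** The strongest reply is that the sign is an editorial slip. The sentence holding it is malformed, every neighbouring statement speaks of a reduction, and no analyst would test for a rise. The formula was also read from PDF by a program, so a misread sign cannot be wholly excluded, though nothing shows one. The likely slip is granted. It is still the stated rule for the primary endpoint, and correcting the sign alone would leave a one-sided null that the table does not reflect.

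A second reply is that sidedness is not really open, because the table points to two-sided 0.05. That also stands. A reader might infer that a one-sided and a two-sided 0.05 test are equally available. The documents do not support that, since no one-sided 0.05 test yields the printed figures. What is lacking is an explicit statement that agrees with the table.

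A reader might also infer that the table is valid only for Fisher's or a continuity-corrected test. That goes too far. Under an uncorrected two-sided test the actual power is 0.827 to 0.959, so the table is then slightly conservative. The matching digits indicate the likely planning method and do not oblige the analysis to use it.

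Finally, the unnamed test, and the modelling that Section 7 announces ("to analyze factors associated with CBPC enrollment and refusal in multivariable statistical modeling (described below") but Section 9 does not describe, are missing detail. They add no weight to this point on their own.

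**Conclusion.** The point holds in two parts. The printed null contradicts the plan's own hypothesis, table and text. Its one-sided form with an unqualified 0.05 also does not match the power calculation, which was evidently done at two-sided 0.05 (or one-sided 0.025).

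A reader might go on to infer an error in the power table or too small a sample. Neither follows. If two-sided 0.05 was used, there is no planning error: all four rows reproduce, and the absolute and percent reductions are arithmetically correct. If one-sided 0.05 was meant, the table understates power (0.877 to 0.896 where 0.80 is stated), and 250 per period remains more than enough for the stated effect.

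The reproduction assumes 250 patients in each period, a pre-intervention rate of 0.32 and independent samples. The last needs care. Section 10 (Aim 3) acknowledges that members offered palliative care before may become eligible again, so some could appear in both periods. The documents do not say how many, so the effect on power cannot be worked out here.

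**What to change.** In Section 9, replace the null with: H0: p_pre = p_post versus H1: p_pre ≠ p_post, two-sided alpha = 0.05. Name the primary test (Fisher's exact or a continuity-corrected test matches the table), and report p_pre − p_post with a 95% CI. State that the two periods are treated as independent samples, and how a member who is eligible in both is counted. The table and the 11.4-point sentence can then stay as they are.

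If a one-sided 0.05 test is intended, write H0: p_pre ≤ p_post versus H1: p_pre > p_post. With continuity correction, restate the detectable rates as 0.218/0.210/0.202/0.189 (reductions of 31.9/34.4/36.9/40.9%) and the 80% power sentence as 10.2 points (31.9%). If one-sided 0.025 is intended, turn the null round in the same way and state that alpha; the table stands.

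The cost is a few sentences in Section 9. The four table rows and the sentence after them change only if one-sided 0.05 is chosen. No new data or patients are needed.
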